3.2 Exclusion Criteria

- 3.2.1 WOCBP who are unwilling or unable to use an acceptable method to avoid pregnancy for the entire study and for up to 26 weeks after the last dose of investigational product.
- 3.2.2 Women who are breastfeeding.
- 3.2.3 WOCBP with a positive pregnancy test within 6 weeks before enrollment.
- 3.2.4 Autoimmune disease: Poorly controlled autoimmune disease is excluded. Well controlled autoimmune disease (e.g. well controlled RA) will be assessed by the study team and a decision made regarding eligibility based on the degree of immunosuppression and severity of symptoms.

- 3.2.5 Any subject who has a life-threatening condition that requires high-dose immunosuppressant(s). Steroid doses greater than 20 mg/day will exclude the patient from participation in the trial.
- 3.2.6 Presence of known hepatitis B or hepatitis C infection, regardless of control on antiviral therapy.
- 3.2.7 Subjects who have another active, concurrent, malignant disease are not eligible, with the exception of subjects with adequately treated basal or squamous cell skin cancer, superficial bladder cancer, carcinoma in situ of the cervix, or other cancers that are in remission/not measurable. Patients will be excluded if they have any known additional malignancy that requires active treatment while on treatment for Merkel Cell Carcinoma.
- 3.2.8 Evidence of symptomatic interstitial lung disease or symptomatic active, noninfectious pneumonitis.
- 3.2.9 Participants with impaired cardiac function or clinically significant cardiac disease such as unstable angina/uncompensated heart failure, uncontrolled symptomatic arrhythmia.
- 3.2.10 Chronic or current active infectious disease requiring systemic antibiotics, antifungal, or antiviral treatment. This exclusion does not include prophylactic antibiotics or topical antibiotics.
- 3.2.11 Known hypersensitivity to another monoclonal antibody, which cannot be controlled with standard measures (e.g. antihistamines and corticosteroids).
- 3.2.12 Any condition that would, in the investigator's judgment, interfere with full participation in the study.
- 3.2.13 Prisoners or subjects who are involuntarily incarcerated.
- 3.2.14 Subjects with acute or poorly controlled psychiatric illness or subjects who are compulsorily detained for physical (e.g., infectious disease) illness, with the exception of patients that are well supported and able to participate (e.g. paraplegia from a motor vehicle accident).
- 3.2.15 Any underlying medical or psychiatric condition that, in the opinion of the investigator, could make the administration of anti-PD-1/PD-L1 hazardous or could obscure the interpretation of adverse events.
- 3.2.16 Any live vaccine therapy for up to 4 weeks before or after any dose of immunotherapy on this trial.

3.3 Informed Consent Process

All participants must be provided a consent form describing the study with sufficient information for participants to make an informed decision regarding their participation.

Participants must sign the IRB approved informed consent prior to participation in any study specific procedure. The participant must receive a copy of the signed and dated consent document. The original signed copy of the consent document must be retained in the medical record or research file.

3.4 Randomization Procedures

Randomization is not used for this open label single arm study.

3.5 Study Timeline

Primary Completion:

The study will reach primary completion 7 ½ years from the time the study opens to accrual.

Study Completion:

The study will reach study completion 7 ½ years from the time the study opens to accrual.

4. TREATMENT PLAN

Screening/Baseline Visit

The following tests and examinations must be performed and the eligibility criteria satisfied before treatment may begin:

- Histologic diagnosis of Merkel Cell Carcinoma
- Demographics and medical history
- Measurements of weight, height, temperature, pulse, respiratory rate, and resting systolic and diastolic blood pressure
- Complete physical examination
- ECOG Performance Status
- Clinical laboratory tests:
 - Hematology: hemoglobin, hematocrit, CBC counts with differential (including absolute lymphocyte count) and direct platelet count
 - Serum Chemistry: albumin, serum alkaline phosphatase, SGOT (AST)/SGPT (ALT), total bilirubin, calcium, creatinine, glucose, lactate dehydrogenase (LDH), total protein, urea nitrogen (BUN), electrolytes (including sodium, potassium, chloride, and bicarbonate), TSH w/Reflex FT4
 - Urinalysis:
 - Gross examination including specific gravity, protein, glucose, and blood
 - Optional microscopic examination including WBC/HPF, RBC/HPF and any additional findings
- Optional Blood sample obtained for investigational immune response assays
- Chest radiography unless baseline CT scan was performed
- Electrocardiogram
- Relevant baseline radiographic images (e.g. brain, chest, abdomen, pelvis, and bone scans with the exact imaging studies utilized determined by the attending physician) within 6 weeks of initiation of anti-PD-1/PD-L1

- Current medications
- Baseline review of symptoms
- Pregnancy test
- Optional Tumor biopsy

Treatment Visits

The day subjects receive the first dose of pembrolizumab therapy will define Day 1. Subjects are required to have blood collected and chemistry labs analyzed up to 1 week prior to each dose of pembrolizumab. Investigators or an assigned medical professional must review liver function tests from the predosing labs and ensure the results meet dosing requirements prior to authorizing administration of each dose of pembrolizumab.

Subjects will receive a single dose of pembrolizumab as standard of care with 200mg IV every 3 weeks (with a -3 and +7-days window) until disease progression or unacceptable toxicity occurs.

During this treatment phase, the following procedures will be performed within 1 week of each scheduled visit:

- Pregnancy test for WOCBP, required within 6 weeks before first dose of pembrolizumab, then optional as clinically indicated for ongoing doses
- Vital sign measurements will include weight, temperature, pulse, and resting systolic and diastolic blood pressure. Vital sign measurements of pulse, and systolic and diastolic blood pressure will be collected prior to the infusion of anti-PD-1/PD-L1.
- Physical examination
- ECOG Performance Status
- Clinical laboratory tests (as outlined in the screening phase) (taken and results reviewed prior to study drug administration):
 - Hematology
 - Serum chemistry
 - TSH w/Reflex FT4- week 13 only (for patients who continue pembrolizumab past week 10)
- Blood (optional) for investigational immune response assays at 2 weeks (± 1 weeks) and 8 weeks (± 1 weeks) after completion of radiation therapy.
- Concomitant medications
- Adverse event assessment
- Optional Tumor biopsy

Follow-up

Patients will be seen for an end of treatment visit 3 weeks (± 1 week) after the last pembrolizumab dose and again for follow up visits every 3 months (± 1 month) for 2 years and then every 6 months (± 1 month) for years 3-4 and again at year 5 (± 1 month) per SOC thereafter until progression of disease by imaging criteria or increased symptomatology that requires another therapy. Follow up visits will be performed until 5 years from the last dose of pembrolizumab and will then become optional and SOC.

The following procedures will be performed at each scheduled follow-up visit ± 1 month during the first 2 years. During years 3-5 the clinical laboratory tests will be performed only once per year.

- Measurements of vital signs (resting systolic and diastolic blood pressure, pulse, respiratory rate, and temperature) and weight
- Physical examination
- ECOG Performance Status
- Clinical laboratory tests
 - Hematology
 - Serum chemistry
 - TSH w/Reflex FT4

- Concomitant medications (for the first 2 years)
- Adverse event assessment (for the first 2 years)
- Status of new and continuing AEs and SAEs (at minimum, collected up to 60 days following last dose of pembrolizumab, 6 months for irSAEs definitely related)
- Relevant imaging studies for tumor measurements
- Optional Tumor biopsy

Survival Follow-Up Assessment for all Subjects

After a subject progresses or changes therapy due to symptomatology, they will enter survival follow-up. In the event a subject withdraws from the treatment phase of the study or discontinues from all other study procedures, the investigators may continue to contact the subject (with his/her agreement) for the collection of survival follow-up data. The subject's decision should be documented in the source records. If possible, contact will be made for all subjects enrolled in the study, regardless of enrollment date. If possible subjects or their caregivers will be contacted every 6 months (± 2 weeks) for 5 years from the last dose of pembrolizumab and inquiries will be made about survival data and/or death date.

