- The appearance of new lesions in subjects with other stable or shrinking baseline tumor burden may be experiencing clinical benefit and should continue on treatment before alternative anti-cancer agents are considered. These subjects can be seen to have continued tumor shrinkage in subsequent imaging.
- As long as overall tumor burden is stable or decreasing, subjects can remain in treatment, even in the presence of new lesions, at the discretion of the treating physician.
- Clinical progression warranting alternative anti-cancer treatment should be considered in subjects whose overall tumor burden appears to be substantially increased and/or in subjects whose performance status is decreased.

- Follow-Up

- Subjects with SD, PR or CR will continue receiving pembrolizumab every 3 weeks per standard of care. After the last dose of pembrolizumab, subjects will enter Follow-Up. Efficacy assessments for these subjects are per standard of care.

- Survival Follow-Up (Post Study Follow-Up)

- Subjects who are no longer receiving pembrolizumab due to unacceptable toxicity (e.g., refractory Grade > 3 AEs), disease progression, investigator judgment, or study closure are managed in survival follow-up.

- If possible, subjects will be contacted or medical records reviewed every 6 months (± 2 weeks) for 5 years after the last dose of pembrolizumab to evaluate survival status.

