9. STUDY CALENDAR

Visits	Pre Study Visit	Treatment Visits					End of Treatment Visit	Follow Up Visit	Post Study Follow Up
	Wk 0	Wk 1 ^h	Btw Wk 1-3	Wk 4	Wk 7	Wk 10	3 Wks after last dose of Pembrolizumab	Every 3, 6M, or at yr 5 from last dose of Pembrolizumab	Upon progression or unacceptable symptomatology
Investigational Agent ^a		X		X	X	X			
Radiation Therapy ^b			X						
Informed consent	X								
Inclusion/Exclusion Criteria	X								

Demographics	X								
Medical history	X								
Physical Exam	X	X		X	X	X	X	X	
Concurrent meds ^c	X	X		X	X	X	X	X	
Vital signs	X	X		X	X	X	X	X	
ECOG Performance status	X	X		X	X	X	X	X	
ECG	X								
Chest Radiography	X								
Adverse event evaluation		X		X	X	X	X	X	
Tumor measurements	X						X	X	
CBC w/diff	X	X		X	X	X	X	X	
Pregnancy Test ^d (Urine or Serum)	X	X		X	X	X			
Hemoglobin	X	X		X	X	X	X	X	
Hematocrit	X	X		X	X	X	X	X	
Metabolic panel, comp	X	X		X	X	X	X	X	
LDH total serum plasma	X	X		X	X	X	X	X	
Urinalysis Macro (Opt Micro)	X								
TSH w/Reflex FT4 ^e	X						X	X	
Optional Immune Response and Polyomavirus Tests ^f	X		X	X		X	X		
Optional Tumor Biopsy ^f	X		X	X	X	X	X	X	
Survival Follow Up ^g									X

a: Investigational Agent- pembrolizumab 200 mg infused SOC every 3 weeks

b: Radiation Therapy- 1-2 sites of disease, delivered between the first and second cycles of pembrolizumab, 9 Gy X 3 (27 Gy in 3 fractions), or 4-6 Gy X 5 (20-30 Gy in 5 fractions)

c: Concurrent meds will be collected until the patient goes off study due to disease progression or change in therapy for Merkel cell carcinoma or for 2 years of continuing response

d: Pregnancy test conducted and negative result confirmed before administration of pembrolizumab in women with the potential to become pregnant, pregnancy test is required ≤ 6 weeks before first dose of pembrolizumab and optional as clinically indicated for ongoing doses

e: Assessed at week 13 for patients who continue pembrolizumab past week 10

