12.3.2 Analysis Plan

Data will be summarized using appropriate descriptive statistics: proportions with Wilson’s 95% confidence intervals, means, standard deviations, ranges, and Kaplan-Meier estimates for time to event data. The toxicity rates will be monitored continuously and a final count of toxicities will be performed.

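### Only one on-treatment TSH is scheduled, at week 13, although pembrolizumab continues every 3 weeks with no maximum

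*Combined protocol and SAP*

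**What the plan says.** Section 4 (Treatment Visits) gives TSH its own line among the treatment-visit laboratory tests: "TSH w/Reflex FT4- week 13 only (for patients who continue pembrolizumab past week 10". Note e to the Section 9 calendar agrees: "Assessed at week 13 for patients who continue pembrolizumab past week 10". The calendar's TSH row is marked at the pre-study, end-of-treatment and follow-up visits, and is empty at weeks 1, 4, 7 and 10.

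Dosing is open-ended. Section 4 gives pembrolizumab "every 3 weeks (with a -3 and +7-days window) until disease progression or unacceptable toxicity occurs", and Section 2.4 adds: "Subjects with SD, PR or CR will continue receiving pembrolizumab every 3 weeks per standard of care". No maximum number of cycles or duration is stated.

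The follow-up visits, which carry TSH, do not overlap with dosing: "After the last dose of pembrolizumab, subjects will enter Follow-Up" (Section 2.4). Section 4 places the end-of-treatment visit 3 weeks (± 1 week) after the last dose. Follow-up visits then run every 3 months (± 1 month) for 2 years, and TSH is on the list introduced by "The following procedures will be performed at each scheduled follow-up visit ± 1 month during the first 2 years".

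**The concern.** As written, thyroid function is tested less often during exposure than after it. Once past week 13, a patient who stays on drug has no scheduled TSH, however long treatment lasts. The same patient, once off drug and not progressing, is tested every 3 months. The plan gives no reason for this ordering.

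Safety is one of the two primary objectives (Section 1.1). Section 7.1.1 lists thyroid gland abnormalities among effects with more than a 5% chance. The planned safety summary is short: "The toxicity rates will be monitored continuously and a final count of toxicities will be performed" (Section 12.3.2). An asymptomatic thyroid event cannot enter that count unless someone orders a test. Without a required schedule after week 13, whether it is found depends on individual practice. Transient events may be missed altogether, and persistent asymptomatic ones may be recognised later than they could be.

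**Working it through.** The plan states no figure to reproduce. The check is a count of visits.

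**Inputs**
- Doses at weeks 1, 4, 7, 10, 13, … (Section 9 calendar, extended every 3 weeks). Dose *n* falls at week 1 + 3(*n* − 1), so week 13 is dose 5.
- Dosing window −3/+7 days (Section 4), so each interval is 18 to 28 days.
- End-of-treatment visit 3 weeks ± 1 week after the last dose, or 14 to 28 days (Section 4).
- Last-dose week: **assumed**, because the documents give no exposure distribution. Weeks 28, 52 and 106 (doses 10, 18 and 36) are used to show a range.

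**Gap from the week-13 TSH to the next scheduled TSH**

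Nominal gap = last-dose week + 3 − 13. With windows, for *k* intervals after dose 5, the gap runs from 18*k* + 14 to 28*k* + 28 days.

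| Last dose | *k* | Nominal gap | With windows (days) | With windows (weeks) |
|---|---|---|---|---|
| Week 28 (dose 10) | 5 | 28 + 3 − 13 = 18 weeks | 104–168 | 14.9–24.0 |
| Week 52 (dose 18) | 13 | 52 + 3 − 13 = 42 weeks | 248–392 | 35.4–56.0 |
| Week 106 (dose 36) | 31 | 106 + 3 − 13 = 96 weeks | 572–896 | 81.7–128.0 |

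If the week-13 blood is drawn a week before its dose, as Section 4 allows, the upper limits become 25.0, 57.0 and 129.0 weeks.

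**Number of scheduled tests.** On drug after Day 1: 1 in all three cases. Off drug without progression: 24 months / 3 = 8 in 2 years, plus the end-of-treatment test.

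**Are such durations plausible?** Section 2.2 describes a single-agent pembrolizumab trial in which 28 of 50 patients responded. Of those 28, 96% responded for at least 6 months and 54% for 12 months or more. Response duration is not exposure, those patients were treatment-naive, and Section 12.2 here expects a 20% response rate, so fewer patients may be affected. Patients with stable disease also continue dosing.

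**Alternative: week 13, then every 4 cycles** (weeks 25, 37, 49, 61, 73, 85, 97, …)
- Added tests: 1, 3 or 7 for a last dose at week 28, 52 or 106.
- Nominal gap from the last on-drug test to end of treatment: 31 − 25 = 6, 55 − 49 = 6 and 109 − 97 = 12 weeks. The longest nominal gap anywhere is 12 weeks.
- With the dosing window, four intervals take 72–112 days, or 10.3–16.0 weeks. Adding 7 days for an early draw gives at most 119 days, or 17.0 weeks. In the week-106 case, the stretch from dose 33 to end of treatment is 3 × 18 + 14 to 3 × 28 + 28 = 68–112 days, or 9.7–16.0 weeks. Withheld doses would lengthen these.

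**The case against.** Two readings of the text would close the gap, and neither holds.
- Section 4 prints TSH on the screening serum chemistry line, and treatment-visit laboratory tests refer back to screening. But the treatment-visit list then gives TSH a separate line limited to week 13, and the calendar cells at weeks 1 to 10 are empty. The specific line governs.
- One synopsis row describes 4 cycles or until progression, which could suggest a four-dose course. The synopsis treatment summary (at least 4 cycles), Sections 2.4 and 4, and the TSH line's own condition about going past week 10 all provide for longer treatment.

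The stronger objection is about purpose. A patient who stops after four doses has the end-of-treatment visit at week 13, so everyone who completes four doses is tested at the same nominal time. Later dosing is standard of care with an approved drug at one institution, and clinicians may well check TSH. Adverse events are still assessed at each treatment visit. No stopping boundary or endpoint depends on low-grade thyroid events, and the endocrinopathy row in Section 6 concerns Grade 3–4 only. Late thyroid change on continued single-agent pembrolizumab says little about whether adding radiation is safe. The 4-cycle interval is a choice, and the lack of a continuation-phase column in the calendar affects more than TSH.

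Much of this stands, and it limits the consequence. It does not remove the gap. The week-13 alignment covers only the first four cycles. In Section 2.4, the standard-of-care wording attaches to dosing and efficacy assessments and does not address thyroid testing. The protocol requires no later test, so ascertainment would not be uniform.

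**Conclusion.** The concern holds. The plan schedules one on-drug TSH and open-ended dosing, which leaves a nominal gap of 18, 42 or 96 weeks for an assumed last dose at week 28, 52 or 106. The number of thyroid events missed cannot be derived from the documents.

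The effect is confined to how completely asymptomatic, low-grade or transient thyroid events after week 13 are counted, and to how early persistent ones are recognised. Grade 3–4 events would probably surface clinically, and a persistent event found at end of treatment still enters the count. Response endpoints, the futility rule and the sample size are unaffected. This is a modest but worthwhile improvement to safety monitoring, recommended because it costs so little. Confidence is medium, since actual exposure and local testing practice are unknown.

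**What to change.** In the treatment-visit laboratory list of Section 4 and in calendar note e of Section 9, replace the single week-13 test with: *TSH with reflex FT4 at week 13 and then every 4 cycles (nominally 12 weeks, subject to visit windows) while dosing continues.* Run it on the blood Section 4 already calls for: "Subjects are required to have blood collected and chemistry labs analyzed up to 1 week prior to each dose of pembrolizumab". Four cycles matches spacing the protocol already uses: Day 1 to week 13 is 12 weeks, and follow-up TSH is every 3 months.

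As a wording clean-up, list TSH separately from serum chemistry in the screening panel, so the cross-reference from treatment visits cannot be misread.

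The cost is a wording amendment at those places and the added assays counted above, for example about 3 per patient with a last dose at week 52. No visit, blood draw, analysis or reporting change is needed.

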4.1 General Concomitant Medication and Supportive Care Guidelines

Concomitant medications/supportive care will be administered per SOC.

4.1.1 Prohibited and/or Restricted Treatments

Subjects in this study may not use live vaccines for the treatment of cancer or prevention of disease (including those for common medical conditions) for up to 4 weeks before and after dosing with Anti-PD-1/PD-L1. Concomitant anti-cancer medications or treatments are prohibited in this study while subjects are receiving Anti-PD-1/PD-L1.

Subjects may not use any of the following therapies during the study:

- Any non-study anti-cancer agent (investigational or non-investigational)
- Any other investigational agents
- Immunosuppressive agents (unless required for treating potential AEs)

- Chronic systemic corticosteroids greater than 20 mg/day (unless required for treating treatment emergent AEs or required for management of signs or symptoms due to brain metastases)
- Any non-oncology live vaccine therapies used for the prevention of infectious diseases (for up to 4 weeks before or after any dose of study drug).

Subjects may be allowed with the following prior therapies:

- Prior treatment with an anti-PD-1/PD-L1 antibody does not exclude patients from this study. Each case will be considered individually and a decision made by the study team. The team will consider if a subject was discontinued from the prior anti-PD-1/PD-L1 treatment due to an AE or SAE. For example, non-clinically significant immune-related laboratory abnormalities – may not automatically exclude patients from participating in this study – e.g. asymptomatic elevated amylase; responsiveness to steroids.
- A history of AEs with prior IL-2 or Interferon will not preclude subjects from entering the current study.

4.2 Criteria for Removal from Study

Subjects MUST discontinue study treatment for any of the following reasons:

- Withdrawal of informed consent (subject’s decision to withdraw for any reason).
- Any clinical AE, laboratory abnormality, or intercurrent illness that, in the opinion of the investigator, indicates that continued participation in the study is not in the best interest of the subject.
- Progressive disease, based on the investigator’s judgment, at or after the end of treatment visit. Progression before the end of treatment visit can be followed by objective response and does not require discontinuation. Small new lesions, by themselves, are not defined as progression.
- Loss of ability to freely provide consent through imprisonment or involuntary incarceration for treatment of either a psychiatric or physical (e.g., infectious disease) illness.

All subjects who discontinue study treatment should comply with protocol-specified follow-up procedures as outlined in Section 4. The only exception to this requirement is when a subject withdraws consent for all study procedures or loses the ability to consent freely (i.e., is imprisoned or involuntarily incarcerated for the treatment of either a psychiatric or physical illness).

If a subject was withdrawn before completing the study, the reason for withdrawal must be entered on the appropriate case report form (CRF) page.

